10.2 SAMPLE SIZE DETERMINATION

To meet objectives of this study we need 50 patients. Considering screen failures, the total number of patients is set at 70 patients.

The sample size is calibrated and determined based on simulation to obtain desirable operating characteristics, as shown in **Table 7**. For example, when the treatment is effective (i.e., PFS6=0.6) for both *RELA*-fusion and Non *RELA*-fusion ependymomas, we have 0.796 chance to conclude that the treatment is effective for both types of ependymomas, and when the treatment is not effective (i.e., PFS6=0.3) for both *RELA*-fusion and Non *RELA*-fusion ependymomas, the probability of incorrectly claiming that the treatment effective is 0.016. Given the sample size of 9 (cohort 1), the 95% confidence interval of PFS6 is not wider than 0.32 on each side. Given the sample size of 16 (Stage 2 cohort 3), the 95% confidence interval of PFS6 and PFS12 is not wider than 0.24 on each side. The two salvage cohorts 2 and 4 are secondary and will not contribute to the statistical power of the study.

The anticipated accrual rate is 1 patient per month for *RELA*-fusion ependymoma cohorts and 1-2 patients per month for the non *RELA*-fusion ependymoma cohorts.

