3 STUDY IMPLEMENTATION

3.1 STUDY DESIGN

3.1.1 Cohorts 1-4:

[figure not shown]
This is a phase II study to evaluate the efficacy of treatment with marizomib in *RELA*-fusion recurrent ependymoma and non *RELA*-fusion recurrent ependymoma. In the stage 1 of study, there will be simultaneous accrual into Cohorts 1 and 2. For Cohort 1, 9 patients with *RELA*-fusion ependymoma and none, 1, or 2 or prior chemotherapies will be enrolled. For Cohort 2, 9 patients with *RELA*-fusion ependymomas and >2 prior chemotherapies. If we find evidence of clinical activity of marizomib, (4 or more patients in Cohort 1 are progression free at 6 months), we will proceed to stage 2, otherwise we will terminate the trial.

At stage 2, we will enroll patients into 2 cohorts: 16 patients with non *RELA*-fusion ependymoma who had none, 1 or 2 prior chemotherapies (Cohort 3) and 16 patients with non *RELA*-fusion ependymoma who had more than 2 prior chemotherapies (Cohort 4).

During stage 2, enrollment into Cohorts 3 and 4 will occur simultaneously. Please see [Schema 1](#).

One cycle is 4 weeks (+/- 3 days). Patients will be treated with IV marizomib at 0.8 mg/m² on days 1, 8 and 15 of each 28-day cycle until off treatment criteria are met (Section 3.8.1).

Schema 1: STUDY DESIGN

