10 STATISTICAL CONSIDERATIONS

10.1 STATISTICAL HYPOTHESIS

The primary objective of this phase II study is to evaluate the efficacy of marizomib in *RELA*-fusion and non *RELA*-fusion ependymoma as measured by the primary endpoint of PFS6. Based on the preclinical data provided in Section 1.2.3 above, we postulate that the clinical activity of marizomib will be greatest in *RELA*-fusion supratentorial ependymoma, which has a constitutional activation of NF-κB pathway. If we see no PFS benefit with marizomib in *RELA*-fusion supratentorial ependymoma patients, then we do not expect that marizomib will benefit the non *RELA*-fusion ependymoma patients. To exploit such efficacy order of the two subgroups (*RELA*-fusion and non *RELA*-fusion), we employ a novel two-stage sequential enrichment design similar to Zang and Yuan (2016) [27]. In the first stage, we will enroll 18 patients with *RELA*-fusion ependymomas to test for clinical activity of marizomib. If 4 or more patients in Cohort 1 are progression free at 6 months, we proceed to stage 2; otherwise we terminate the trial and conclude that marizomib is not effective. Additionally, during stage 1, we will allow patients harboring *RELA*-fusion ependymoma with more extensive exposure to chemotherapy (> 2 chemotherapy regimens) to enroll. Given the preclinical data, this will enable this patient population to have access to a treatment regimen when most of the commonly used therapies have already been utilized. The responses of this group (Cohort 2) are a secondary objective and will not be used to make the determination of efficacy and will not be used for deciding to proceed to stage 2. However, the response results will be compiled as preliminary data regarding efficacy of marizomib as a salvage regimen for patients with heavily pretreated *RELA*-fusion ependymoma. At stage 2, we will enroll 16 patients with non *RELA*-fusion ependymomas (Cohort 3). Out of these 16 patients, if 9 or more patients are progression free at 6 months, we claim that marizomib is promising for treating both *RELA*-fusion and non *RELA*-fusion ependymoma; otherwise, we claim that marizomib is promising for treating *RELA*-fusion, but not for non *RELA*-fusion ependymoma. Based on historical data and clinical experience, we regard 30% of PFS6 as unpromising, and 60% of PFS6 as promising. The following table shows the operating characteristics of the above design based on 10,000 simulations.

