Table 7. Operating characteristics of the two-stage sequential enrichment design

True PFS6 of RELA -fusion ependymomas	True PFS6 of	Probability of early stopping	Probability of claiming	Probability of claiming	Average sample size

	Non RELA- fusion ependymomas		effective for RELA -fusion	effective for all patients	
0.3	0.3	0.734	0.265	0.016	13.2
0.6	0.6	0.102	0.898	0.796	23.4
0.6	0.3	0.102	0.898	0.167	23.4
0.6	0.5	0.102	0.898	0.632	23.4

The study of salvage cohorts 2 and 4 is a secondary objective.

As patients in salvage cohorts 2 and 4 are highly heterogeneous, the efficacy of marizomib in *RELA*-fusion cohort 2 may not be notably higher than that in non *RELA*-fusion cohort 4. The objective of cohorts 2 and 4 is to estimate the efficacy of marizomib in recurrent ependymoma patients with multiple prior chemotherapies as measured by PFS6, PFS12, median PFS and OS. As a result, the 2-stage design will not be used for cohorts 2 and 4. Instead, we enroll patients into these cohorts simultaneously.

10.1.1 Primary Endpoint:

- Progression-free survival at 6 months of *RELA*-fusion and non *RELA*-fusion recurrent ependymoma patients treated with marizomib (Cohorts 1-4) will be assessed as proportion of patients that are progression-free at 6 months timepoint after initiation of treatment.

10.1.2 Secondary Endpoint(s):

- Progression-free survival at 12 months of *RELA*-fusion and non *RELA*-fusion recurrent ependymoma patients treated with marizomib (Cohorts 1-4) will be assessed as proportion of patients that are progression-free at 12 months timepoint after initiation of treatment
- Median progression-free survival (PFS) of *RELA*-fusion and non *RELA*-fusion recurrent ependymoma patients treated with marizomib (Cohorts 1-4) will be assessed as median amount of time subject survives without disease progression after initiation of treatment
- Overall survival (OS) of *RELA*-fusion and non *RELA*-fusion recurrent ependymoma patients treated with marizomib (Cohorts 1-4) will be assessed as median amount of time subject survives after initiation of therapy
- Progression-free survival at 6 months of *RELA*-fusion and non *RELA*-fusion recurrent ependymoma patients with with more than 2 prior chemotherapies treated with marizomib (Cohorts 2 and 4) will be assessed as proportion of patients that are progression-free at 6 months timepoint after initiation of treatment.

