10.4.4 Planned Interim Analyses

Two-stage sequential enrichment design will be used for this trial. In the first stage, we will enroll 9 patients with *RELA*-fusion ependymomas (Cohort 1) to test for clinical activity of marizomib. If 4 or more patients are progression free at 6 months, we proceed to stage 2; otherwise we terminate the trial and conclude that marizomib is not effective. At stage 2, we will enroll 32 patients with non *RELA*-fusion ependymomas (Cohort 3 and 4). From Cohort 3, if 9 or more of 16 patients are progression free at 6 months, we claim that marizomib is promising for treating both *RELA*-fusion and non *RELA*-fusion ependymoma; otherwise, we claim that marizomib is promising for treating *RELA*-fusion, but not for non *RELA*-fusion ependymoma. As above, PFS-6 for Cohort 4 will also be measured in patients with non-*RELA* fusion ependymoma that has been extensively treated. These data will be compiled as preliminary data regarding efficacy of marizomib as a salvage regimen for patients with heavily pretreated non-*RELA*-fusion ependymoma.

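### Table 7's all-patients column, and the 0.796 and 0.016 that section 10.2 takes from it, do not follow from the written decision rule, under which power for the both-types claim is 0.645

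*Combined protocol and SAP*

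**What the plan says.** The rule has two steps. For the first, section 3.1.1 requires that "4 or more patients in Cohort 1 are progression free at 6 months", and section 10.4.4 agrees: "If 4 or more patients are progression free at 6 months, we proceed to stage 2". Cohort 1 has 9 patients (sections 3.1.1, 10.2 and 10.4.4). For the second, section 10.1 bases the claim for both tumour types on Cohort 3: "Out of these 16 patients, if 9 or more patients are progression free at 6 months". Section 10.4.4 repeats it: "From Cohort 3, if 9 or more of 16 patients are progression free at 6 months". If the second step fails, the claim is limited to RELA-fusion disease. Section 10.1 takes a PFS6 of 30% as unpromising and 60% as promising.

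Table 7, titled "Operating characteristics of the two-stage sequential enrichment design" and based on 10,000 simulations, gives the probability of claiming efficacy for all patients as 0.016, 0.796, 0.167 and 0.632. The corresponding true PFS6 pairs (RELA-fusion, non RELA-fusion) are (0.3, 0.3), (0.6, 0.6), (0.6, 0.3) and (0.6, 0.5).

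Section 10.2 relies on this column. It says "The sample size is calibrated and determined based on simulation to obtain desirable operating characteristics", cites 0.016 as the probability of a wrong claim when neither type benefits, and states that "we have 0.796 chance to conclude that the treatment is effective for both types of ependymomas".

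**The concern.** Table 7 conflicts with the written rule before anything is recalculated. If the second step uses Cohort 3 alone, then once stage 1 has been passed the chance of the both-types claim depends only on the non RELA-fusion rate. Two rows of the table share a non RELA-fusion rate of 0.3, so dividing the all-patients probability by the probability of passing stage 1 should give the same value in both. It gives 0.016/0.265 = 0.060 in one and 0.167/0.898 = 0.186 in the other. The simulated rule must therefore have used Cohort 1 outcomes in the second step as well.

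Two things are at stake. The power used to justify the sample size may belong to a rule the trial will not apply. And if the simulated rule was the intended one, the text misstates the primary decision, so the same data could support opposite conclusions about non RELA-fusion disease.

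**Working it through.** **Inputs.** Cohort 1: n = 9, go if X ≥ 4. Cohort 3: n = 16, both-types claim if Y ≥ 9. Cohorts 2 and 4 play no part (sections 10.1 and 10.2). Patients are treated as independent, each with a known 6-month status.

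**Formulas.** With p₁ the RELA-fusion and p₂ the non RELA-fusion PFS6:
- P(go) = P(X ≥ 4 | 9, p₁)
- P(both types) = P(go) × P(Y ≥ 9 | 16, p₂)
- average N = 9 + 16 × P(go)

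**Step 1: the columns that reproduce.** P(go) is 0.2703 at p₁ = 0.3 and 0.9006 at p₁ = 0.6.

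| Quantity | p₁ = 0.3: exact | Table 7 | p₁ = 0.6: exact | Table 7 |
|---|---|---|---|---|
| Early stopping | 0.730 | 0.734 | 0.099 | 0.102 |
| RELA-fusion claim | 0.270 | 0.265 | 0.901 | 0.898 |
| Average N | 13.3 | 13.2 | 23.4 | 23.4 |

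The probabilities agree within 1.2 simulation standard errors. This confirms the sample sizes 9 and 16 and the stage 1 cutoff of 4.

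**Step 2: the column that does not.** P(Y ≥ 9 | 16, p₂) is 0.0257, 0.4018 and 0.7161 for p₂ = 0.3, 0.5 and 0.6. The last column of the table below divides the gap by the standard error of the printed value, √(p(1−p)/10,000).

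| (p₁, p₂) | Written rule, exact | Table 7 | Gap in standard errors |
|---|---|---|---|
| (0.3, 0.3) | 0.2703 × 0.0257 = 0.007 | 0.016 | 7.2 |
| (0.6, 0.6) | 0.9006 × 0.7161 = 0.645 | 0.796 | 37.5 |
| (0.6, 0.3) | 0.9006 × 0.0257 = 0.023 | 0.167 | 38.6 |
| (0.6, 0.5) | 0.9006 × 0.4018 = 0.362 | 0.632 | 56.0 |

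**Step 3: the internal check.** The two conditional probabilities at p₂ = 0.3 are 0.0604 (standard error 0.0046) and 0.1860 (standard error 0.0041). They differ by 0.1256, about 20 standard errors. The written rule gives 0.0257 in both rows.

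**Step 4: which rule would give the printed column?** No other cutoff on Cohort 3 alone fits. At least 8 of 16 gives 0.020, 0.773, 0.067, 0.539. At least 7 of 16 gives 0.047, 0.848, 0.158, 0.696. A pooled rule, X ≥ 4 and X + Y ≥ 13 of 25, has probability Σ over x ≥ 4 of P(X = x | 9, p₁) × P(Y ≥ 13 − x | 16, p₂). It gives 0.0151, 0.7995, 0.1626 and 0.6235, all within 1.8 standard errors of Table 7. Pooled totals of 12 (0.035, 0.857, 0.285, 0.743) and 14 (0.006, 0.704, 0.081, 0.477) do not fit.

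**Step 5: consequence at (0.6, 0.6).** Under the written rule the trial claims RELA-fusion only with probability 0.9006 − 0.6449 = 0.256. Table 7 implies 0.898 − 0.796 = 0.102.

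**The case against.** One defence is that stage 1 is described in section 10.1 as enrolling 18 patients, so the inputs could have been misread. It fails: the 18 are Cohorts 1 and 2 together, Cohort 2 is excluded from the go decision, and the early-stopping and average-sample-size columns reproduce with 9. Damage to the table in the PDF is no explanation either, because section 10.2 repeats 0.796 and 0.016 in prose.

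A stronger point is that the operational rule is clear and stated consistently. The mismatch changes no patient's treatment, the stage 1 gate or enrolment. That is true, but section 10.2 rests the sample size on these figures.

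The false-claim rates are also lower under the written rule than printed (0.007 against 0.016, and 0.023 against 0.167). That holds only for the both-types claim. When neither type benefits, the chance of some efficacy claim is the stage 1 pass rate, 0.270 (Table 7: 0.265), under either rule. Section 10.2 words its 0.016 as though it covered any claim.

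Two cautions stand. The pooled rule is inferred from fit to four numbers; no section states it, and the cited design paper was not available. The (0.6, 0.5) row is a sensitivity case, since the plan sets 0.6 as its target.

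**Conclusion.** The concern holds. The written rule and the all-patients column of Table 7 cannot both be right. If the text stands, power for the both-types claim is 0.645, about 15 points below the stated 0.796, and the corresponding null probability is 0.007, not 0.016. At a non RELA-fusion PFS6 of 0.5, the both-types claim would more often be missed than made (0.362, against 0.632 printed).

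If the table reflects the intended rule, the text omits that Cohort 1 successes count towards the claim for non RELA-fusion disease. Under the inferred 13-of-25 rule, that claim could be made with 5 of 16 in Cohort 3 after 8 of 9 in Cohort 1 (8 + 5 = 13), or with 4 of 16 after 9 of 9. The written rule would reject both.

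The mismatch itself rests only on the documents' own rule, sample sizes and table, with independent binomial outcomes. The identity of the simulated rule is an inference. The early-stopping, RELA-fusion and average-sample-size columns are not affected.

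**What to change.** Reconcile the rule and the table before any Cohort 3 outcome is seen.

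- **If the written rule stands:** replace the all-patients column of Table 7 by 0.007, 0.645, 0.023 and 0.362. In section 10.2, give power 0.645 and null probability 0.007, both labelled as applying to the both-types claim. Put the chance of about 0.27 of some efficacy claim under the null beside the 0.007, so that the smaller figure is not read as the overall error rate.
- **If a pooled rule was intended:** write it identically in sections 10.1 and 10.4.4. State that Cohort 1 successes count towards the non RELA-fusion claim. Disclose the false-claim rate for that type at (0.6, 0.3): 0.167 as printed, or 0.163 exact if the rule is 13 of 25.

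The cost is a text and table correction with no extra patients. Keeping the written rule means accepting a less favourable stated power, with lower stated false-claim rates for the both-types claim. The remaining columns of Table 7 need no change.

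### Section 10.2 gives 0.016 as the false-claim probability, but that covers only a claim for both tumour types; the probability of any false efficacy claim is 0.27

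*Combined protocol and SAP*

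**What the plan says.** Section 10.1 sets the benchmarks: "we regard 30% of PFS6 as unpromising, and 60% of PFS6 as promising". Cohort 1 (9 RELA-fusion patients) decides stage 1. With fewer than 4 progression free at 6 months the trial stops and the drug is declared not effective; with 4 or more it goes on to Cohort 3 (16 non RELA-fusion patients). Section 10.4.4 gives the condition for claiming activity in both tumour types: "From Cohort 3, if 9 or more of 16 patients are progression free at 6 months". If that condition fails, Section 10.1 still makes a claim: "otherwise, we claim that marizomib is promising for treating" RELA-fusion disease, but not the other type.

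Table 7 is presented as "the operating characteristics of the above design based on 10,000 simulations". Its row for PFS6 of 0.3 in both types shows early stopping 0.734, a RELA-fusion claim 0.265 and an all-patients claim 0.016.

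Section 10.2 refers to Table 7 and then summarises it. On power, at PFS6 of 0.6 in both types, "we have 0.796 chance to conclude that the treatment is effective for both types of ependymomas". On error, at PFS6 of 0.3 in both types, "the probability of incorrectly claiming that the treatment effective is 0.016". The power statement says which claim it concerns. The error statement does not.

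**The concern.** If the drug is inactive in both types, a claim limited to RELA-fusion disease is just as false as a claim for both. As worded, the 10.2 sentence should cover either claim, but 0.016 covers only the second.

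This matters because RELA-fusion disease is the lead hypothesis: Section 10.1 expects the greatest activity there. Section 10.2 is also where a reader looks for the error rate behind the sample size. Taken at its word, it offers 1.6%, while the design calls an inactive drug promising for RELA-fusion disease about 27% of the time.

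A second question follows at once. If the sentence is to be mended by naming the joint claim, the joint figure itself has to be the one the written rule produces.

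**Working it through.** **Inputs.** Stage 1: X ~ Bin(9, p1), pass if X ≥ 4 (10.1, 10.4.4). Stage 2: Y ~ Bin(16, p2), joint claim if Y ≥ 9 (10.1, 10.4.4). Unpromising 0.3, promising 0.6 (10.1). 10,000 simulations (10.1). Cohort 2 plays no part in the decision (10.1).

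**Step 1: reproduce the stage 1 columns of Table 7.**
- P(X ≥ 4 | 9, 0.3) = 0.2703, so early stopping = 1 − 0.2703 = 0.7297. Table 7: 0.265 and 0.734.
- P(X ≥ 4 | 9, 0.6) = 0.9006, so early stopping = 0.0994. Table 7: 0.898 and 0.102.
- Average sample size = 9 + 16 × P(pass) = 13.33 and 23.41. Table 7: 13.2 and 23.4.

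The simulation standard error at 0.2703 is √(0.2703 × 0.7297 / 10,000) = 0.0044, so the tabled 0.265 lies 1.2 standard errors away. These columns agree with the written rule. Reading stage 1 as 4 of all 18 RELA-fusion patients would give 0.835 at 0.3, so n = 9 is the basis of the table.

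**Step 2: probability of any false claim.** Every trial that passes stage 1 ends in a claim. Table 7 bears this out, since early stopping plus the RELA-fusion claim adds to 1 within rounding in each row (0.734 + 0.265 = 0.999; 0.102 + 0.898 = 1.000). Hence, at PFS6 of 0.3 in both types, P(any false claim) = P(X ≥ 4 | 9, 0.3) = **0.2703**, against 0.016 in the text of 10.2. On the tabled figures, (0.265 − 0.016) / 0.265 = 0.249 / 0.265 = 94% of false claims are for RELA-fusion disease alone, and the sentence leaves these out.

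**Step 3: check the joint figure.** P(joint claim) = P(X ≥ 4) × P(Y ≥ 9), with P(Y ≥ 9 | 16, p2) = 0.0257, 0.7161 and 0.4018 at p2 = 0.3, 0.6 and 0.5.

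| True PFS6 (RELA, non RELA) | Written rule | Table 7 | Gap in simulation SEs |
|---|---|---|---|
| 0.3, 0.3 | 0.2703 × 0.0257 = 0.0069 | 0.016 | 11 |
| 0.6, 0.6 | 0.9006 × 0.7161 = 0.645 | 0.796 | 32 |
| 0.6, 0.3 | 0.9006 × 0.0257 = 0.023 | 0.167 | 96 |
| 0.6, 0.5 | 0.9006 × 0.4018 = 0.362 | 0.632 | 56 |

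The all-patients column does not follow from the written rule, and no Cohort 3 cut-off from 6 to 10 of 16 fits all four rows. For illustration only: a pooled rule, X ≥ 4 and X + Y ≥ 13 of 25, gives 0.0151, 0.7995, 0.1626 and 0.6235, each within 1.8 standard errors of the table. The documents state no such rule, so this is an inference from the fit.

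**Step 4: what a boundary result would show.** At 4 of 9 the 95% interval is 0.137 to 0.788 (exact) or 0.444 ± 0.325 = 0.120 to 0.769 (Wald). Both include 0.30.

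**The case against.** The best defence is that nothing is hidden. Section 10.2 points to Table 7, the table has its own RELA-fusion column showing 0.265, and the preceding clause is about both types, so an attentive reader may carry that qualifier over. On this view a few words are missing and the number was copied correctly. That the larger rate is disclosed stands. It does not rescue the sentence, whose wording covers a RELA-only claim that its number excludes.

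It is also fair to say that the plan sets no alpha for this rule, that its claim is only that the drug is promising, and that 0.27 may be an acceptable false-positive rate in a small phase II trial of a rare tumour. This stands, and it is why the stage 1 rule is not in question.

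The ratio of 0.270 to 0.016, about 17, should not be pressed, because it compares two different events. The wide interval at 4 of 9 comes from the sample size, not from the wording of 10.2: even 6 of 9 has an exact lower limit of 0.299. Section 10.4.1 already plans a 95% interval for PFS6.

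Finally, the conflict between Table 7 and the 9-of-16 rule can be called a separate matter. The 0.27 indeed does not depend on it, since any claim needs only a stage 1 pass. But the repair does depend on it: adding the qualifier alone would leave 0.016 and 0.796 standing as joint figures that the written rule does not produce.

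**Conclusion.** The concern holds and should be fixed. With PFS6 of 0.3 in both types, the probability of any false efficacy claim is 0.270 exactly (0.265 as simulated), not 0.016. This rests on the written stage 1 rule with n = 9, on all 9 patients being classifiable at 6 months, and on independent outcomes; it does not depend on which stage 2 rule was meant. The fault is a misstated summary in 10.2, not concealment.

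The joint figures in the same sentence are also unsupported by the plan's own rule. At least 9 of 16 gives a joint false claim of 0.007 against 0.016 stated, and joint power of 0.645 against 0.796 stated. Whether the table or the written rule is in error cannot be settled from the documents.

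**What to change.** 1. Restate the error sentence in 10.2 with both rates, for example: *When true PFS6 is 0.3 in both types, the probability of a false efficacy claim for at least RELA-fusion disease is about 0.27 (Table 7: 0.265), and the probability of a false claim for both types is [joint figure].*
2. Before filling in the joint figure and re-confirming 0.796, reconcile Table 7 with the stage 2 rule. If at least 9 of 16 is intended, rerun Table 7; the joint figures become about 0.007 and 0.645. If another rule was simulated, write that rule into 10.1 and 10.4.4.
3. Report any RELA-fusion conclusion together with the Cohort 1 95% interval, and name the interval method.

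The cost is one sentence, plus a simulation rerun or a correction of the written rule. No patients are added and the stage 1 rule is unchanged. The price is a less favourable stated error rate and, if 9 of 16 is confirmed, stated joint power falling from 0.796 to 0.645.
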